5.5. Administration

Subjects receiving blinded study medication will be dispensed two (2) bottles at each dispensing visit and given clear dosing instructions. Subjects should be instructed to take one (1) tablet from each bottle in the morning and one (1) tablet from each bottle in the evening, approximately 12 hours apart. Subjects receiving blinded study medication will therefore be taking two (2) tablets twice a day, regardless of which blinded treatment arm they are randomized to receive.

If a subject has their tofacitinib dose **adjusted to open-label 5 mg BID** due to having any of the risk factors for venous thromboembolism, they will be dispensed **only one (1)** bottle of 5 mg tablets and should be instructed to take one (1) tablet from the bottle in the morning and one (1) tablet in the evening, approximately 12 hours apart. Therefore, subjects will only be taking one (1) tablet twice a day if the tofacitinib dose is adjusted to open-label 5 mg BID.

If a tofacitinib dose is missed and the interval to the next scheduled dose is less than 6 hours, the missed dose of tofacitinib should not be administered. Tofacitinib may be taken with or without food. Subjects will swallow the investigational product whole and will not manipulate or chew the investigational product prior to swallowing.

Table 1. Investigational Product Administration

Treatment Assignment	AM Dosing*	PM Dosing*
5 mg BID (blinded)	Bottle A 5 mg - 1 tablet Bottle B Placebo – 1 tablet	Bottle A 5 mg - 1 tablet Bottle B Placebo – 1 tablet
10 mg BID (blinded or open-label)	Bottle A 5 mg - 1 tablet Bottle B 5 mg - 1 tablet	Bottle A 5 mg - 1 tablet Bottle B 5 mg - 1 tablet
5 mg BID (open-label)	Bottle A 5 mg - 1 tablet	Bottle A 5 mg - 1 tablet

* Bottle A and B designations are used for example purposes only.

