Once the subject is confirmed to meet the definition for flare, documented by site read endoscopy, the investigator may adjust the dose through the IRT system provided that the subject does not have any of the risk factors for venous thromboembolism (see [Section 7.3.6](#)). Once confirmed by the investigator, subjects may have a dose increase to 10 mg BID or remain on 10 mg BID, depending on their initial treatment assignment. Dose adjustments for confirmed flare will not be permitted prior to the Month 1 study visit.

Subjects who develop one or more of the risk factors for venous thromboembolism during the study will not be permitted to increase their tofacitinib dose to 10 mg BID should they experience a flare of their UC.

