9.2.3. Secondary Analysis

Dose comparison between tofacitinib 5 mg BID and 10 mg BID

For the primary objective, the treatment difference for the binary secondary efficacy endpoints will also be estimated based on the FAS, using the same approach as described above for the primary endpoint. For continuous endpoints, the change from baseline will be analyzed using linear mixed-effects model with baseline value, dose group, the endoscopic

subscore at baseline (0 versus 1), visit, and dose group by visit interaction all as fixed effects, and subject as a random effect. The adjusted estimations and associated 95% CI for the overall difference between the two dose groups will be computed. Kaplan-Meier estimates at the scheduled visits will be computed for time to event endpoint. The log-rank test stratified by endoscopic subscore at baseline (0 versus 1) will also be performed for the comparison between dose groups.

If a subject has a dose escalation back to tofacitinib 10 mg BID, then

- For binary efficacy endpoints, the subject will be considered as a non-responder for any visit after the dose escalation visit.
- For continuous efficacy endpoints, the data collected for any visit after the dose escalation visit will be considered as missing.
- For time to loss of remission, the subject will be considered as having an event at the visit with a dose escalation if the event criteria are met or having a censor time at the visit with a dose escalation if the event criteria are not met.

For continuous endpoints that are measured repeatedly over time, the missing values will be handled in a linear mixed-effects model where the *mechanism of missingness* is assumed to be missing at random.

Regimen comparison between flexible dosing and fixed dosing

For the first secondary objective, analyses will be performed based on the FAS for comparisons of the following two dose regimens:

- Tofacitinib fixed 10 mg BID Dose Regimen: subjects who are initially assigned to tofacitinib 10 mg BID at randomization and stay on tofacitinib 10 mg BID until completion or discontinuation.
- Tofacitinib flexible 5 mg/10 mg BID Dose Regimen: subjects who are initially assigned to tofacitinib 5 mg BID at randomization, staying on tofacitinib 5 mg BID or having dose escalation from tofacitinib 5 mg BID to 10 mg BID.

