3.2. Secondary Endpoints

- Time to loss of remission (flare) based on modified Mayo score. Loss of remission (flare) is defined as meeting at least one of the 4 criteria for flare above in [Section 2.2](#).
- Remission based on modified Mayo score at scheduled visits other than Month 6 for dose groups.
- Remission based on modified partial Mayo score. Remission based on modified partial Mayo score is defined as stool frequency subscore of 0 or 1, and a rectal bleeding subscore of 0.
- Remission based on total Mayo score. Remission based on total Mayo score is defined as total Mayo score of 2 points or lower, with no individual subscore exceeding 1 point and a rectal bleeding subscore of 0.

- Remission based on partial Mayo score. Remission based on partial Mayo score is defined as partial Mayo score of 2 points or lower, with no individual subscore exceeding 1 point and a rectal bleeding subscore of 0.
- Change from baseline (of Study A3921288) in modified Mayo score.
- Change from baseline (of Study A3921288) in modified partial Mayo score.
- Change from baseline (of Study A3921288) in total Mayo score.
- Change from baseline (of Study A3921288) in partial Mayo score.
- Mucosal healing. Mucosal healing is defined as an endoscopic subscore of 0 or 1.
- Clinical response based on total Mayo score. Clinical response based on total Mayo score is defined as decrease from baseline in total Mayo score of the Induction study, of at least 3 points and at least 30%, with an accompanying decrease in the subscore for rectal bleeding of at least 1 point, or absolute subscore for rectal bleeding of 0 or 1.
- Change from baseline in fecal calprotectin and change from baseline in hs-CRP levels.

CCI

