5.3. Methods to Manage Missing Data

5.3.1. Efficacy Endpoints

For binary efficacy endpoints derived from total Mayo score or partial Mayo score, subjects with missing scores in an analysis window will be considered as non-responders.

For continuous endpoints that are measured repeatedly over time, the missing values will be handled in a linear mixed effects model where missing values are assumed to be missing at random.

For continuous endpoints based on total Mayo score and modified Mayo score, data collected after baseline to Month 6 will be considered as Month 6 if a subject has missing data at Month 6; data collected after Month 6 to Month 18 will be considered as Month 18 if a subject has missing data at Month 18; data collected after Month 18 to Month 30 will be considered as Month 30 if a subject has missing data at Month 30; data collected after Month 30 to Month 42 will be considered as Month 42 if a subject has missing data at Month 42. The description of the handling of missing data within individual components of the Mayo score is described in an [Appendix 2.1](#).

Subjects who drop out or complete the study without meeting the flare criteria will be censored at the last visit with Mayo score assessment for endpoint of time to loss of remission (flare).

Descriptive summary will also be presented based on observed data for efficacy data.

For the subgroup of subjects who are initially assigned to tofacitinib 5 mg BID and later are retreated with tofacitinib 10 mg BID, missing data will not be imputed.

For fecal calprotectin and hs-CRP, the missing values will be handled in a linear mixed effects model where missing values are assumed to be missing at random.

In addition, for hs-CRP, assayed values below the limit of quantification (BLQ) will be set to 10% less than the given assay lower limit for the specific biomarker. In listings BLQ values will be reported as “<LLQ” where LLQ will be replaced with the value for the lower limits of quantification. Assay values will be set to missing if a value has been collected as ND (ie, not done) or NS (ie, no sample).

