5.3.3. Method of Handling the Data after Dose Escalation or Dose Reduction

For this study, subjects may have a dose escalation to 10 mg BID due to flare or dose reduction to 5 mg BID due to PE risk factors. The data after the dose change for the dose group and regimen group are handled as follows.

- For Tofacitinib 10 mg BID dose group: For subjects with dose reduction due to PE risk factor, data collected after the dose reduction will not be included in the safety and efficacy analyses, and last observation carried forward (LOCF) will be used for binary and continuous efficacy endpoints. The subjects will be considered as censored at the dose reduction time for endpoint of time to loss of remission (flare).
- For Tofacitinib 5 mg BID dose group: data collected after the dose escalation (with or without dose reduction due to PE risk factor after the dose escalation) from tofacitinib 5 mg BID to 10 mg BID will not be included in the safety and efficacy analyses. The subjects will be treated as non-responders for any visit after the dose escalation visit for binary efficacy endpoints. For continuous efficacy endpoints, the data collected for any visit after the dose escalation visit will be considered as missing. For time to loss of remission (flare), the subject will be considered as having an event at the visit with a dose escalation if the event criteria are met or having a censored time at the visit with a dose escalation if the event criteria are not met.
- For Tofacitinib 10 mg BID regimen group: For subjects with dose reduction due to PE risk factor, data collected after the dose reduction will be included in the safety and efficacy analyses.

- For Tofacitinib 5 mg BID regimen group: Data collected after the dose escalation will be included in the analyses. For subjects with dose reduction due to PE risk factor after the dose escalation, data collected after the dose reduction will be included in the safety and efficacy analyses.

The following table provides some examples on how to handle the data after the dose escalation for flare and dose reduction for risk factors for PE:

Table 2 Examples on How to Handle Data After Dose Change

Examples	Dose group		Regimen group	
	Safety analysis	Efficacy analysis	Safety analysis	Efficacy analysis

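### In the dose-group analysis of time to loss of remission, an escalation that fails the derived flare criteria censors a 5 mg subject, while a 10 mg subject given the same blinded adjustment stays at risk

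*SAP*

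**What the plan says.** **Event.** SAP Section 3.2: "Loss of remission (flare) is defined as meeting at least one of the 4 criteria for flare above in" SAP Section 2.2. Protocol Section 5.11 uses the same four criteria to permit a dose adjustment. It requires flare to be confirmed first, with a site-read endoscopy.

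**The adjustment.** The site makes it through the IRT. Protocol Section 5.11 says that "subjects may have a dose increase to 10 mg BID or remain on 10 mg BID, depending on their initial treatment assignment". SAP Section 2.2 adds that the assignment stays blinded, so the same site action can occur in either arm. Table 1 in Protocol Section 5.5 lists 10 mg BID supply in both blinded and open-label form.

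**5 mg dose group.** Under SAP Section 5.3.3, an escalated subject has an event at that visit if the criteria are met; otherwise the subject is recorded as "having a censored time at the visit with a dose escalation if the event criteria are not met". Protocol Section 9.2.3 has the same rule: "having a censor time at the visit with a dose escalation if the event criteria are not met".

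**10 mg dose group.** SAP Section 5.3.3 covers only dose reduction for pulmonary embolism risk, which censors the subject at the reduction. It has no rule for a flare adjustment that leaves the dose at 10 mg. The general rule in SAP Section 5.3.1 then applies: "Subjects who drop out or complete the study without meeting the flare criteria will be censored at the last visit with Mayo score assessment".

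**Binary endpoints, same 5 mg escalation.** "The subjects will be treated as non-responders for any visit after the dose escalation visit for binary efficacy endpoints".

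**The concern.** One blinded site decision has two consequences in this endpoint. If the derived criteria are not met, the 5 mg subject leaves the risk set that day. The 10 mg subject stays in it, and a later flare counts. A site that enters a flare adjustment presumably believes the disease is worsening, so the censored 5 mg subjects are probably not a random sample of those still at risk. Kaplan-Meier and log-rank methods assume that they are.

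The same 5 mg escalation is a failure at every later visit in the binary endpoints, so the two sets of results could diverge for a reason unrelated to dose. SAP Section 5.2.1 plans sensitivity analyses for binary remission; Section 5.2.4 plans none for time to event.

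Time to loss of remission is the first-listed secondary endpoint. Amendment 1 extended the study to 42 months partly to allow more time for efficacy in the two dose groups to diverge, and this curve would show that.

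**Working it through.** **1. The plan's own figures.** The documents give no flare rate, no hazard ratio and no rate of adjustment without the criteria. The only precision figure concerns the primary endpoint: a half width of about 16% with 65 per group and remission above 70%. It reproduces as 1.96 × √(2 × 0.70 × 0.30 / 65) = 15.75%, but does not bear on this point.

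**2. Can the censored branch be reached?** A fully compliant escalation meets the event criteria and is an event. Endoscopy is read locally only, so there is no central read to disagree with the site. Three gaps remain:
- The criteria require an increase in subscores, but neither document names the reference visit.
- Protocol Section 7.2.3 bases the score on diary data from the 3 prior consecutive days. SAP Appendix 2.1 excludes bowel-preparation days, uses the most recent available days within 5, rounds the average, and sets the subscore to missing if there is no diary entry in that period.
- A site may adjust the dose without full confirmation, which is a deviation.

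**3. Closed-form check on one arm at a time.** Assume that 35% of subjects have a flare adjustment by Month 18, with a constant hazard and no drop-out. Let *f* be the share of adjustments that do not meet the criteria.
- 5 mg, discordant adjustments censored: 1 − 0.65^(1−*f*).
- 10 mg, discordant subjects left at risk and none flaring later: 0.35 × (1−*f*).
- 10 mg, all of them flaring by Month 18: 35%.

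| *f* | 5 mg | 10 mg, none flare later | 10 mg, all flare by Month 18 |
|---|---|---|---|
| 10% | 32.1% | 31.5% | 35% |
| 20% | 29.2% | 28.0% | 35% |
| 30% | 26.0% | 24.5% | 35% |

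The sign of the gap between arms depends on how many adjusted 10 mg subjects later meet the criteria.

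**4. Simulation of both arms.** The settings were 1,500 runs per cell, 70 per arm (138 were enrolled at Amendment 2), exponential times and an unstratified two-sided 5% log-rank test. Three inputs are assumptions, not taken from the documents:
- 40% loss of remission by Month 42 on 10 mg, and 20% random drop-out;
- *f* from 5% to 30%, equal in both arms;
- *q*, the chance that a discordant subject left at risk later meets the criteria (mean delay 3 months).

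Before drop-out, 70 × 0.40 = 28 worsening subjects per arm, so *f* = 5% is 1.4 subjects and *f* = 30% is 8.4.

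Median hazard ratio, 5 mg versus 10 mg, under the SAP rule with no true difference:

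| *q* | *f* = 5% | 10% | 20% | 30% |
|---|---|---|---|---|
| 1 | 0.96 | 0.90 | 0.81 | 0.71 |
| 0.5 | 1.00 | 0.97 | 0.93 | 0.87 |

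At *q* = 0 the ratio runs from 1.02 (*f* = 5%) to 1.09 (*f* = 30%).

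At *f* = 20% and *q* = 1, the Month 42 loss-of-remission estimates are 33.5% (5 mg) and 39.5% (10 mg). The test favours 5 mg in 10.5% of runs, against a nominal 2.5%. With a true hazard ratio of 1.8, the same cell gives 1.47, and the chance of showing 5 mg worse is about 30%, against 66% when the adjustment counts as an event in both arms.

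Counting the adjustment as an event in both arms gives 0.99 to 1.01 under no difference and 1.76 to 1.83 under a true ratio of 1.8.

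**The case against.** The strongest reply is that the branch should be nearly empty. Adjustment and endpoint share the same four criteria, flare must be confirmed first, and endoscopy has a single local reader. This stands as a limit on frequency. It does not make the rule idle, because both documents provide for an escalation whose criteria are not met.

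A second reply is that censoring suits a primary objective about subjects who remain on 5 mg, and that a 10 mg subject who leaves 10 mg for embolism risk is censored too. Failure in the binary endpoints and censoring in the time-to-event endpoint can be two legitimate strategies. This also stands: the difference between endpoints is not an error in itself. It does not explain why the same blinded adjustment is handled by arm.

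A reader might infer more than the documents support:
- **That sites escalate on impression alone.** The confirmation requirement rules this out for compliant escalations.
- **That the 5 mg estimate falls with no matching fall on 10 mg.** Step 3 shows the 10 mg estimate can fall slightly further.
- **That perceived failures leave the 5 mg curve only.** Withdrawals for rescue therapy without flare are censored in both arms; the asymmetry concerns the escalation route alone.

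**Conclusion.** The asymmetry is in the text, and nothing in either document removes it. The 10 mg half is an inference from the absence of a rule for that arm, together with the default in SAP Section 5.3.1.

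Its effect is uncertain. The rate of discordant adjustments is not given, and the direction depends on what those subjects would have done next. Under the stated assumptions and no true difference, the hazard ratio lies between 0.96 and 1.02 at 5% discordance, which is negligible with about 70 per arm. Over rates up to 30% it lies between 0.71 and 1.09. A large distortion needs both frequent discordance and a high chance of later flare. It would be wrong to state flatly that the curves are tilted toward 5 mg.

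The reach is one secondary endpoint in the dose-group comparison. The regimen comparison keeps data after escalation, the primary endpoint is separate, and SAP Section 5.1 tests no formal hypothesis. A sensitivity analysis is warranted; replacing the planned analysis is not.

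**What to change.** Leave the planned analysis as it is and add to SAP Sections 5.2.4 and 5.3.3:

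1. A count, by dose group, of IRT flare adjustments that did not meet the derived criteria, including those for 10 mg subjects who remained on 10 mg. If the count is near zero, the point is closed.
2. A sensitivity Kaplan-Meier and stratified log-rank analysis in which the IRT flare adjustment is an event on its date in both dose groups, again including 10 mg subjects who remained on 10 mg.

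Specify both before final database lock. SAP Section 7.1 has the sponsor's study team unblinded from the Month 6 analysis, so the text should give the date of the addition and apply one rule to both arms.

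The cost is one extra run and a few lines of SAP text. Adjustments are made through the IRT, so the dates should already exist. In that run the event departs from the strict four-criteria definition, so it must be labelled a sensitivity analysis. No clinical rule changes.

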5.2. General Methods

For the primary objective, analyses will be performed for comparisons of the following two dose groups:

- Tofacitinib 10 mg BID dose group: subjects who are initially assigned to tofacitinib 10 mg BID at randomization
- Tofacitinib 5 mg BID dose group: subjects who are initially assigned to tofacitinib 5 mg BID at randomization, regardless of whether the dose is escalated back to tofacitinib 10 mg BID or not (Data collected after the dose escalation from tofacitinib 5 mg BID to 10 mg BID will not be included in the analyses.)

For the first secondary objective, analyses will be performed for comparisons of the following two regimen groups:

- Tofacitinib 10 mg BID regimen group: subjects who are initially assigned to tofacitinib 10 mg BID at randomization.
- Tofacitinib 5 mg BID regimen group: subjects who are initially assigned to tofacitinib 5 mg BID at randomization, staying on tofacitinib 5 mg BID or having dose escalation from tofacitinib 5 mg BID to 10 mg BID. Data collected after the dose escalation will be included in the analyses.

For the second secondary objective, summary descriptive statistics will be reported for the subgroup of subjects who are initially assigned to tofacitinib 5 mg BID and later are re-treated with tofacitinib 10 mg BID based on the observed case data using the original windowing rules. In addition, the efficacy data after the dose escalation will be summarized using the new windowing rule by resetting the baseline (Day 0) at the dose escalation time.

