5.3.2. Safety Endpoints

Missing data for safety endpoints will not be imputed.

For dose groups, data collected after the dose escalation will not be included in the analyses. For regimen group, data from subjects with dose escalation back to tofacitinib 10 mg BID will be treated as it is.

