5 mg->10 mg at Month X	Data after Month X will not be included	Data after Month X will not be included. Subjects will be treated as non-responders after Month X for binary, and missing for continuous endpoints	Data after Month X will be included	Data after Month X will be included
10mg->5 mg at Month X	Data after Month X will not be included	Data after Month X will not be included. LOCF will be used	Data after Month X will be included	Data after Month X will be included.
5mg->10mg at Month X->5mg at Month Y	Data after Month X will not be included	Data after Month X will not be included. Subjects will be treated as non-responders after Month X for binary, and missing for continuous endpoints	Data after Month X(including data after Month Y) will be included	Data from Month X (including data after Month Y) will be included.

At the time of finalizing SAP V2, all subjects completed Month 6 and no subjects had dose reduction before Month 6. The data handling rules for dose reduction will not be applied for the primary analysis performed at Month 6, however they will be applied to the final analysis performed at the end of the study.

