For dose groups, IR will be calculated only for adverse events of special interest only. The numerator will be the number of unique subjects with a treatment emergent event as defined above during the interval from the first dose in A3921288 study to dose adjustment for dose escalated or dose reduced subjects otherwise to last dose + 28 days at risk period. The denominator of the incidence rate is person time accruing from the subject's first dose to day of dose escalation, or the first dose to day of dose reduction, or last dose + 28 days, or to the date of the first event, whichever occurs earlier. For a subject who died, the time will be the minimum of dose escalation day, dose reduction day, the day of the last dose + 28 days, or death day.

However, for mortality (death), malignancies (including NMSC), malignancies (excluding NMSC) and MACE related endpoints, all events regardless of their onset within 28 days or beyond after the last dose of tofacitinib will be included. The concept of 28 days is applied to subjects without events that discontinued or completed the study.

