7. INTERIM ANALYSES

7.1. Introduction

The data collected from this study will be analyzed at two time points.

The primary analysis will be performed to assess efficacy and safety when all subjects enrolled complete their Month 6 study visit (or drop out before Month 6 visit) and data are cleaned and locked. The primary analysis will include efficacy data up to Month 6 and safety data up to the data cutoff date, and will be performed only for dose group comparison. This will be considered as the primary completion date. The initial treatment assignments at baseline will remain double-blinded to the site and subject (i.e., Pfizer will not provide the individual subject treatment/randomization codes to the sites until the study is completed). The Pfizer study team will become unblinded at the time of the Month 6 primary analysis and will remain unblinded for the duration of the study. The Argus Safety Database will not be unblinded for the primary analysis. Results from the primary analysis may be shared with Regulatory Authorities and may be published for scientific presentation.

The final analysis will be performed when all subjects complete the study and the database is cleaned and locked. This secondary analysis will be performed for all efficacy endpoints and safety endpoints and for dose group, regimen group and the subgroup of subjects who escalate their dose from tofacitinib 5 mg BID back to tofacitinib 10 mg BID.

An external data monitoring committee (E-DMC) will be responsible for ongoing monitoring of the safety of subjects in the study according to the DMC charter. The recommendations made by the E-DMC to alter the conduct of the study will be forwarded to Pfizer for final decision. Pfizer will forward such decisions, which may include summaries of aggregate analyses of endpoint events and of safety data that are not endpoints, to regulatory authorities, as appropriate.

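### The SAP waives its dose-reduction rule for the whole Month 6 primary analysis, but primary safety runs to the data cutoff, so any later events on open-label 5 mg would count under 10 mg

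*SAP*

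**What the plan says.** SAP 5.3.3 sets a rule for subjects in the 10 mg dose group whose dose is reduced because of a pulmonary embolism risk factor: "data collected after the dose reduction will not be included in the safety and efficacy analyses". The example table in the same section repeats the exclusion in its safety column for dose groups.

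The section closes by suspending the rule for one analysis: "The data handling rules for dose reduction will not be applied for the primary analysis performed at Month 6". The reason comes just before: "At the time of finalizing SAP V2, all subjects completed Month 6 and no subjects had dose reduction before Month 6". The rules are then said to apply to the final analysis.

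SAP 7.1 defines the span of the primary analysis: "The primary analysis will include efficacy data up to Month 6 and safety data up to the data cutoff date". It adds that this analysis "will be performed only for dose group comparison", and that its results may go to regulators or be published.

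Three other places bear on the point:

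- SAP 5.2 forms the group by randomisation: "Tofacitinib 10 mg BID dose group: subjects who are initially assigned to tofacitinib 10 mg BID at randomization".
- SAP 5.3.2, like 5.2.5, limits dose-group safety data only at escalation: "For dose groups, data collected after the dose escalation will not be included in the analyses".
- SAP 6.6.1 counts dose-group person-time for adverse events of special interest "from the subject's first dose to day of dose escalation, or the first dose to day of dose reduction", among other end points, and makes no exception for the primary analysis.

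**The concern.** The reason for the waiver and the reach of the waiver do not match. The absence of reductions before Month 6 makes the rule idle for data that end at Month 6. The primary safety data do not end there. For safety between Month 6 and the cutoff, the waiver removes a rule that may still have work to do.

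The two arms would then be treated differently in one table. A 5 mg subject who escalates is cut at escalation, while a 10 mg subject who is reduced is followed through. The 10 mg column could include events that arose on 5 mg, in subjects selected because they carry thromboembolic risk factors. The final dose-group tables would treat the same subjects and dates the other way. Since the primary results may be released on their own, a reader could meet the two versions without an explanation.

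**Working it through.** **Figures in the plan.** The plan gives no number for dose reductions. Its one precision figure is a half width of about 16% for the Month 6 remission difference, with 65 per group. It reproduces at a remission rate of 70%: 1.96 × √(2 × 0.70 × 0.30 / 65) = 0.158. It concerns efficacy only and does not enter this point.

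**Tracing the text.** These are the consequences for each dose path in the dose-group comparison:

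| Randomised dose and later path | AE proportions, primary analysis | AE proportions, final analysis | Incidence rates, special-interest events |
|---|---|---|---|
| 10 mg, reduced to open-label 5 mg after Month 6 and before the cutoff | Post-reduction events stay under 10 mg (5.3.3 waiver; 5.2.5 and 5.3.2 cut only at escalation) | Excluded (5.3.3) | 5.3.3 waives the rule; 6.6.1 stops at reduction: conflict |
| 5 mg, escalated to 10 mg | Cut at escalation | Cut at escalation | Stops at escalation |
| 5 mg, escalated, then reduced | Cut at escalation | Cut at escalation | Stops at escalation |
| 5 mg, moved to open-label 5 mg | Dose unchanged, no misattribution | Same | Same |

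Only the first row is a problem.

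**How much the stated reason tells us.** The risk-factor check came with Amendment 2, dated 19 June 2019. Protocol 9.1 says that about 122 of 138 subjects had then passed Month 6: 122 / 138 = 88%. For them, a reduction under that procedure could not have preceded Month 6. The statement that none did therefore says little about later reductions.

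**Longest post-reduction time.** SAP V2 is dated 11 March 2020. From 19 June 2019 that is 266 days, and 266 / 30.44 = 8.7 months. If the cutoff lies near the SAP V2 date (an assumption), 8.7 months is the most that one subject could contribute after a reduction. Subjects reduced later contribute less.

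**Effect on a proportion.** Assume equal arms: 138 / 2 = 69 subjects. The dose group is as randomised, so the denominator stays the same and only the numerator moves. One reduced subject whose first event of a given type came after the reduction adds 1 / 69 = 1.4 percentage points to the 10 mg proportion. Two such subjects add 2.9 points and three add 4.3. A subject who already had that event before the reduction adds nothing.

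**Effect on a rate, only if the waiver were held to override 6.6.1.** All of these inputs are assumptions: 1 to 7 subjects reduced, 3 to 8.7 months each, and 69 to 103.5 person-years in the arm.

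- Low end: 1 × 3 / 12 = 0.25 person-years; 0.25 / 103.5 = 0.2% of exposure.
- High end: 7 × 8.7 / 12 = 5.1 person-years; 5.1 / 69 = 7.4% of exposure.
- For an assumed true 10 mg to 5 mg rate ratio of 2.0, the ratio seen is 2.0 × (1 − f) + 1.0 × f, where f is the share of exposure after reduction. At f = 0.074 this is 1.93; at f = 0.002 it is 2.00.

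**The case against.** The strongest reply is that the waiver was meant for efficacy only. Its reason speaks of Month 6, and the analysis it names is the one performed at Month 6. That may well be the intention. But the sentence suspends the rules as a whole for the primary analysis, and those rules explicitly cover safety. A programmer following it would leave the exclusion out of the safety tables. If efficacy only was meant, the sentence still needs the limit written in.

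A second reply is that little depends on it. This largely stands. No formal hypotheses are tested, the tiered adverse event analysis is declared exploratory, a listing of reduced subjects is planned, and the final analysis applies the rule. These facts limit the harm, but they do not make the primary safety tables agree with the final ones.

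Some stronger readings are tempting, and the documents do not support them:

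- A reader might infer that 5 mg events are in fact sitting in the 10 mg column. The documents give no count of reductions after Month 6, no events following one, and no cutoff date.
- A reader might infer that 10 mg person-time is contaminated. SAP 6.6.1 ends dose-group person-time at the reduction, so for those rates there is a conflict between sections and not an established error.
- A reader might take the interval from Amendment 2 to SAP V2 as the least 5 mg time per reduced subject. It is an upper value if the cutoff is near the SAP V2 date. It would require a reduction on the date of the amendment, whereas risk factors were also to be checked at each later visit.

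**Conclusion.** The point holds as a mismatch in the text. The waiver in 5.3.3 is wider than the reason given for it, because primary safety extends past Month 6 to the cutoff. If any 10 mg subject was reduced in that interval, later events would be counted under 10 mg in the adverse event proportions and other non-rate safety summaries, contrary to the rule for the final analysis. For incidence rates of special-interest events, 5.3.3 and 6.6.1 give opposite instructions.

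The size cannot be fixed from the documents. It is probably small and may be zero. The figure of about 1.4 points per affected subject rests on an assumed 69 per arm. The ceiling of about 8.7 months per subject rests on a cutoff near the SAP V2 date. The primary efficacy result and the design precision do not change.

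**What to change.** In SAP 5.3.3, limit the waiver to Month 6 efficacy and state the safety rule. For example: *Because no reduction preceded Month 6, the dose-reduction rules have no effect on primary efficacy. For safety up to the cutoff, the exclusion after a dose reduction applies to the 10 mg dose group in the primary analysis in the same way as in the final analysis.*

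Then reconcile 5.3.3 with 6.6.1 and 7.1, so that proportions, other safety summaries and incidence rates all stop at the same point for a reduced subject. It would help to add the dose-reduction cut to 5.2.5 and 5.3.2, which now mention only escalation.

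The cost is a sentence or two in the SAP and a date filter that the final analysis needs anyway. The downside is that a little post-reduction data leaves the primary dose-group safety tables. The planned listing still identifies the subjects concerned, and the regimen-group safety analysis at the end of the study includes their data.
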